Statistical Analysis for the MedStar Diabetes Pathway Ongoing Chart Review Protocol. (June 1, 2016).

The study was powered to detect a difference of 0.5 in the change in HbA_{1c} with SD=2 with 80% power at alpha=0.05 with a sample size of 128 in each group (paired t-test). The study reaches 100% power to detect this observed difference (1.6, SD=2.25, post-hoc) with an alpha level of 0.01. Data were summarized using means and standard deviations for continuous variables and frequencies and percentages for categorical variables. Differences in patient characteristics and the unadjusted differences in the outcome measures between the intervention and control groups were tested using linear mixed models, McNemar tests, and conditional logistic models due to matching (Tables 2 and 3). The significance of the comparison between the groups of their respective within group risk change from pre to post-intervention was determined by longitudinal Poisson models that include time and group interactions. Multivariable Poisson regression models adjusted for pre-intervention utilization, baseline HbA_{1c}, age, and sex were used to estimate post-intervention 30-day and 90-day hospital admission and ED visit risk for participants compared to controls (Table 3). The average decrease in HbA_{1c} among men compared to women was examined using a mixed model that included an interaction with sex and group.

Pre-intervention differences between the groups in utilization outcomes were computed and tested using unadjusted Poisson regression models. Analyses were conducted in R 3.1.0 (R Core, Vienna, Austria) (31) and Stata 14 (StataCorp, College Station, TX) (32).

We also conducted an analysis to examine potential for monetization of the intervention benefits from reduced inpatient services to the health system. Based on the expected times of hospitalization per patient in 90 days for both the intervention group and comparison group, estimated by the Poisson regression model, we projected the annual difference in usage of inpatient services between a patient with and without the intervention. The projected change in usage was then multiplied by the expense per diabetes associated hospitalization, which was calculated from the actual claims data of the health system's employee health plan in Year 2017 to be \$25,162.95 per hospitalization.

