- Patient satisfaction with the MDP

In addition, the clinical team will also compare the clinical and utilization outcomes of patients enrolled in the MDP with those of a randomly selected control group consisting of MedStar

patients with elevated A1C levels. This will be done to allow a better assessment of the impact and effectiveness of the MDP.

Once the data is obtained, it will be de-identified prior to data analysis and reporting. Demographics will be reported as a group, i.e. percentage of patients within a certain age group or geographic area or with a certain type of insurance to insure equal access to the MDP, and help recruit underrepresented groups so they can also benefit from the program.

Data Management

The MedStar Health Research Institute will provide data management services for all aspects of the chart review process, including preparation of the program REDCap database, quality checks of data and developing processes for bringing data into REDCap from available data sources held by system partners which will be leveraged for the program. All data will be de-identified prior to presentation to the Biostatistician for analysis.

Data Analysis and Reporting Plan

Data analysis will be performed by the MHRI Biostatistician. All data will be de-identified prior to submission to the biostatistician for analysis. Results will be reviewed for quality improvement purposes and will also be presented at national meetings. Additionally, one or more manuscripts will be prepared for submission to peer-reviewed journals.

References

1- Management of Hyperglycemia in Type 2 Diabetes: A Patient-Centered Approach

Position Statement of the American Diabetes Association (ADA) and the European Association for the Study of Diabetes (EASD). [Silvio E. Inzucchi](#), MD,¹ [Richard M. Bergenstal](#), MD,² [John B. Buse](#), MD, PHD,³ [Michaela Diamant](#), MD, PHD,⁴ [Ele Ferrannini](#), MD,⁵ [Michael Nauck](#), MD,⁶ [Anne L. Peters](#), MD,⁷ [Apostolos Tsapas](#), MD, PHD,⁸ [Richard Wender](#), MD,⁹ and [David R. Matthews](#). Diabetes Care. 2012 Jun; 35(6): 1364–1379.

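### HbA1c change in non-randomised groups is tested without covariate adjustment inside an undescribed matched design; add an adjusted model as a sensitivity analysis

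*SAP*

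**What the plan says.** The SAP is a short text without numbered sections. Its first paragraph covers everything relevant here.

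- **Planned power.** The study was sized for a difference of 0.5 in HbA1c change "with SD=2 with 80% power at alpha=0.05 with a sample size of 128 in each group (paired t-test").
- **HbA1c comparison.** The "unadjusted differences in the outcome measures between the intervention and control groups were tested using linear mixed models". The same sentence goes on to McNemar tests and "conditional logistic models due to matching", so the comparison is unadjusted but made within matched data.
- **Utilization.** Poisson models "adjusted for pre-intervention utilization, baseline HbA_{1c}, age, and sex were used to estimate post-intervention 30-day and 90-day hospital admission and ED visit risk".
- **The only other HbA1c model.** A "mixed model that included an interaction with sex and group". It asks whether the effect differs by sex, and no baseline HbA1c is listed for it.
- **Post-hoc statement.** The study is said to reach "100% power to detect this observed difference (1.6, SD=2.25, post-hoc) with an alpha level of 0.01".

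The protocol's section III (Chart Review and Data Collection) says outcomes will be compared with "those of a randomly selected control group consisting of MedStar" "patients with elevated A1C levels. This will be done to allow a better assessment". It gives no matching variables, ratio or A1C limit for controls. Program patients must have an A1C of at least 9.0% (Inclusion Criteria). The only matching scheme set out anywhere is the pilot's (protocol, Background): 1:3 on age, sex, race/ethnicity, insurance group and baseline A1C.

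**The concern.** Patients who start with a higher A1C tend to fall further, partly through regression to the mean and partly because usual care responds to a high value. The protocol's Background makes the second argument itself to explain the fall among pilot controls. In a non-randomised comparison, a difference in baseline A1C therefore passes directly into the difference in change. If controls could enter with A1C below 9%, program patients would start higher and the unadjusted difference would favour the program.

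Matching on baseline A1C would largely prevent this, but the documents do not say that the current controls were matched on it. The SAP's authors held baseline HbA1c, age and sex and thought them worth adjusting for in the utilization models. The powered outcome has no corresponding model. What is at stake is the size and interval of the reported 1.6-point difference more than its existence.

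**Working it through.** **1. The plan's own figure.** Inputs from the SAP: difference 0.5, SD 2, alpha 0.05 (taken as two-sided), 128 per group, paired t-test. With SD 2 as the SD of the within-pair difference, the noncentrality is 0.5/2 × √128 = 2.83 on 127 df. Power is 80.15%; at 127 pairs it is 79.84%. The stated 128 and 80% reproduce.

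**2. How strongly change depends on baseline.** The documents give no slope, so I derive one from the SDs in the protocol's Table 1, assuming that they carry over to the later study.

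Covariance of baseline and 3-month A1C = (SD_base² + SD_3m² − SD_change²)/2. Slope of change on baseline = covariance/SD_base² − 1.

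| | SD base | SD 3 m | SD change | Covariance | r | Slope |
|---|---|---|---|---|---|---|
| Cases | 1.86 | 1.52 | 2.01 | 0.865 | 0.31 | −0.75 |
| Controls | 1.71 | 1.98 | 1.97 | 1.482 | 0.44 | −0.49 |

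The pooled slope is −0.63. Table 1 may not describe the same patients throughout (11.35 − 8.31 = 3.04, but the change is given as 3.08), so I carry the range of slopes.

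**3. Shift in the unadjusted difference = imbalance × slope.**

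| Baseline imbalance (points) | Shift (points) |
|---|---|
| 0.06 (pilot: 11.41 − 11.35) | 0.03–0.05 |
| 0.25 | 0.12–0.19 |
| 0.5 | 0.25–0.38 |
| 1.0 | 0.49–0.75 |

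In the other direction, an imbalance of 0.5/0.75 = 0.67 to 0.5/0.493 = 1.01 points would produce the whole planned difference of 0.5. An imbalance of 1.6/0.75 = 2.13 to 1.6/0.493 = 3.24 points would be needed to produce 1.6.

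**4. What adjustment does, and what it assumes.** I simulated 128 unmatched patients per group with the pooled slope and no true effect.

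| Assumption | Imbalance | Unadjusted rejection | Baseline-adjusted rejection |
|---|---|---|---|
| Both groups share one dependence on absolute baseline | 0.5 | about 24% | about 5% |
| | 1.0 | about 71% | about 5% |
| Each group regresses to its own mean | 0.5 | about 5% | about 35% |
| | 1.0 | about 5% | about 84% |

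Which estimate is biased depends on an assumption that these documents cannot settle. That is the reason to report both.

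**5. If controls were in fact unmatched.** A two-sample t-test with 128 per group, SD 2 and difference 0.5 has 51.3% power, and 80% needs 253 per group. These figures do not apply to the matched design that the SAP describes.

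**6. Precision of the reported result.** If 128 pairs were analysed and 2.25 is the SD of the paired difference, SE = 2.25/√128 = 0.199, and the 95% CI is 1.6 ± 1.979 × 0.199 = 1.21 to 1.99.

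**The case against.** The strongest reply is that matching is itself control of confounding. The comparison is unadjusted only within matched sets, and the one scheme described, the pilot's, already covers baseline A1C, age and sex. The only documented baseline comparison is also close, and there the controls start slightly higher, which would work against the program. Much of this stands. It explains why the likely shift is small. It does not close the point, because nothing says that the pilot scheme was carried forward. The pilot used 1:3 matching, whereas the SAP sizes two equal groups.

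Two further replies also stand. Baseline adjustment is not a guaranteed correction in non-randomised groups, as step 4 shows, so the adjusted model belongs beside the unadjusted one and should not replace it. The SAP also says that patient characteristics were compared, and it cites tables that are not part of these documents. Those tables may already show baseline HbA1c by group.

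A reader might infer that the protocol and SAP contradict each other on how controls were chosen, that true power was about 51%, or that the false-positive rate was 24% or 71%. The documents do not support these readings. Controls can be drawn at random from among eligible matches, although neither document says so. The power loss would need unmatched controls. The false-positive rates would also need an imbalance of 0.5 or 1.0 points, which no passage reports.

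**Conclusion.** The point holds as a gap in the analysis that is cheap to close. The powered outcome has no overall model adjusted for baseline HbA1c, age and sex, and the matching that might make one unnecessary is not described. The consequence is a shift of about 0.49 to 0.75 in the unadjusted difference per point of baseline imbalance, assuming that the pilot SDs apply and that both groups share the same dependence on absolute baseline. With pilot-like balance the shift is 0.03 to 0.05. The 1.6 difference is unlikely to be explained by baseline A1C alone.

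The 80% power claim is correct for 128 matched pairs and is not an error. The description of controls and the post-hoc power sentence are reporting matters that change no result. Power computed at the observed difference adds nothing to the estimate and says nothing about its precision.

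**What to change.** **Main change.** Add to the SAP, labelled as post hoc because the unadjusted result was already known:

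> HbA1c change was also compared using a linear mixed model with group, baseline HbA1c, age and sex as fixed effects and a random effect for matched set. Adjusted and unadjusted differences are reported side by side with 95% confidence intervals, the adjusted model as a sensitivity analysis.

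Check a baseline-by-group term, with baseline centred, because the pilot slopes differ (−0.75 v −0.49). Add baseline HbA1c to the sex-by-group model. Report mean baseline HbA1c by group, or point to the table that gives it.

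**Minor reporting changes.** Bring the protocol's description of controls into line with the SAP by naming the matching variables, the ratio and the A1C limit for controls. Replace the post-hoc power sentence with the estimate, the number of pairs analysed and the 95% CI (about 1.21 to 1.99 under the assumptions in step 6). State that SD 2 refers to the paired difference, and give its source.

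**Cost.** One extra model on variables already collected, a few sentences, and no new patients or data. The drawbacks are that the model is post hoc, that it rests on the shared-dependence assumption, and that its estimate may be smaller than 1.6. If matching on A1C was close, it will simply confirm the result.

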Ninety-eight (98) patients with uncontrolled type 2 diabetes have completed the MedStar Diabetes Pathway Boot Camp. A1C, a measure of average blood glucose control over the 2-3 months prior to the test being done, was checked at baseline and then after 3 months follow-up. Admissions and resource utilizations were measured for the period 6 months before baseline and then recorded between baseline and 3 months and between 3 months and 6 months. For comparison of A1C improvement, patients were matched to controls at a 1:3 ratio on age, sex, race/ethnicity, insurance group, and baseline A1C. The difference in improvements of A1c between a case and its matched control was tested. Utilization has not yet been captured for controls.

Clinical and Health Resources Utilization Outcomes.

- **A1C Performance.**

Blood glucose control improvement, as measured by change in A1C results is shown below.

Table 1: Change in A1C

	Boot Camp Cases	Control Cases	P value
Baseline A1C (%)	11.35 (1.86)	11.41 (1.71)	0.439
3 month A1C (%)	8.31 (1.52)	9.77 (1.98)	<0.001
Change in A1C (%)	-3.08 (2.01)	-1.64 (1.97)	<0.001
Percent A1C lowering	27%	14%	

The 3.08 % lowering of A1C among Boot Camp patients is highly clinically important. In comparison, most drug trials where A1C lowering is measured, there is typically reduction in A1C of 0.5-1.5% depending upon the drug or drugs being tested¹. Furthermore, a 1% absolute reduction in A1C can be correlated with an approximately 15% reduction in risk for myocardial infarction². The fact that lowering in A1C was also seen among control cases is not completely unanticipated. Per current standard care, when a patient presents with a markedly elevated A1C the physician caring for him/her would implement measures to help improve control which explains the concurrent fall in A1C over time. These results show that the Boot Camp intervention effectively doubled A1C lowering when compared to controls.

- **Health Resource Utilizations.**

Utilization for urgent care visits, urgent PCP visits, hospitalizations, and Emergency Department (ED) visits due to diabetes, taken in the 6 months before the listed time is shown in Table 2.

Table 2. Health Resource Utilizations

	Baseline (n)	3 months		6 months		P value
	Number	Number	% Reduction	Number	% Reduction	
Urgent Care Visits	3	0		0		0.109
Urgent PCP Visits	13	1	91%	1	92%	0.002
Hospitalizations	9	1	88%	3	66%	0.207
ED Visits	18	1	94%	2	88%	<0.001

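### The Poisson models for hospital and ED use state no allowance for overdispersion or matched sets, and do not settle whether the outcomes are counts or any visit; the effect on error rates depends on visit rates and dispersion that the documents do not give.

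*SAP*

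**What the plan says.** The SAP describes three Poisson analyses of utilization:

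- Changes from before to after the intervention are compared between groups with "longitudinal Poisson models that include time and group interactions".
- Multivariable models, adjusted for prior utilization, baseline HbA1c, age and sex, "were used to estimate post-intervention 30-day and 90-day hospital admission and ED visit risk for participants compared to controls".
- Pre-intervention group differences "were computed and tested using unadjusted Poisson regression models".

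No variance estimator, dispersion term or matched-set term is stated for any of them. For other comparisons, the unadjusted outcome differences among them, the SAP does respond to the design: these were "tested using linear mixed models, McNemar tests, and conditional logistic models due to matching".

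The outcome is called a risk in the multivariable model. The cost projection, however, takes a count from the Poisson model: "Based on the expected times of hospitalization per patient in 90 days". Section III of the protocol lists only ED and hospital visits in 30-day and 90-day windows.

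The control group is described in three ways. Section III of the protocol compares participants "with those of a randomly selected control group". The SAP's power statement uses a paired t-test with 128 per group. The protocol Background says that "patients were matched to controls at a 1:3 ratio", but that is the pilot. The Background also says of the pilot: "Utilization has not yet been captured for controls".

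**The concern.** ED visits and admissions tend to cluster in a few patients, so counts often vary more than a Poisson model allows. If the default variance is used, standard errors are then too small and the test rejects too often. If the outcome is instead any visit (yes or no), the Poisson variance exceeds the binomial variance and the test is conservative. Ignoring positive correlation within matched pairs is also conservative for a between-group comparison. These errors pull in different directions, and the text does not say which applies.

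At stake are the intervals and p-values of the hospital and ED comparison, which is intended for publication. The variance choice does not change the point estimate in the cost projection.

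**Working it through.** **The plan's own figure.** The only sample-size statement concerns HbA1c: difference 0.5, SD 2, 80% power, alpha 0.05 (two-sided assumed), paired t-test. The noncentral t distribution gives 80.15% power at n = 128, and the normal approximation (2 × (1.960 + 0.842)/0.5)² gives 126. The 128 is reproduced. No power or error rate is stated for utilization.

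**Inputs.** Protocol Table 2 gives 18 ED visits and 9 hospitalizations in the 6 months before baseline. The denominator is assumed to be the 98 pilot patients, and 6 months is taken as 182.5 days. The SAP gives 128 per group.

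**Rates.** Mean per patient = events/98 × days/182.5. With frailty variance k, the variance-to-mean ratio is 1 + k × mean. For an any-visit outcome, the ratio of true to Poisson-model variance is about exp(−mean).

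| Outcome | Mean | Expected events per 128 | Count ratio, k = 2 / 5 | Any-visit ratio |
|---|---|---|---|---|
| ED, 90 days | 0.091 | 11.6 | 1.18 / 1.45 | 0.91 |
| Admissions, 90 days | 0.045 | 5.8 | 1.09 / 1.23 | 0.96 |
| ED, 30 days | 0.030 | 3.9 | 1.06 / 1.15 | 0.97 |
| Admissions, 30 days | 0.015 | 1.9 | 1.03 / 1.08 | 0.985 |

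**Simulated size of a nominal 5% Wald test.** Assumptions: no true effect, 128 pairs, gamma frailty with variance 2 or 5 (assumed), within-pair frailty correlation 0 or 0.6 (assumed). There were 20,000 runs per unadjusted cell and 8,000 per adjusted cell. A group with zero events counts as a non-rejection. Adjustment is for log(1 + prior count) only; HbA1c, age and sex were not simulated.

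| Counts | Default, unadjusted | Default, adjusted | Clustered, unadjusted | Clustered, adjusted |
|---|---|---|---|---|
| ED, 90 days | 5.3-9.6% | 5.2-7.8% | 4.8-5.8% | 4.9-5.8% |
| Admissions, 90 days | 3.0-4.1% | 3.0-3.8% | 2.7-3.6% | 2.9-4.1% |
| ED, 30 days | 1.2-1.5% | 1.0-1.5% | 1.0-1.5% | 1.3-2.6% |
| Admissions, 30 days | 0.04-0.08% | 0.04-0.11% | 0.04-0.24% | 0.4-1.4% |

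For 90-day ED counts with default variance, the four cells (k, correlation) = (2, 0), (2, 0.6), (5, 0), (5, 0.6) give 6.3, 5.3, 9.6 and 6.9% unadjusted, and 5.8, 5.2, 7.8 and 5.9% adjusted. Correlation lowers the size in each case.

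**Where the result changes:**

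- *Little dispersion:* at k = 0 the 90-day ED size is 4.3%; at k = 1 it is 5.5% (correlation 0) or 4.8% (correlation 0.6).
- *Pair correlation alone:* with a shared pair frailty of variance 1 and nothing else, it is 4.2%.
- *Any visit instead of count:* 90-day ED is 2.3-3.7% by default and 3.9-4.2% clustered.
- *Pilot post-baseline rates:* Table 2 shows 1 and 2 ED visits after baseline. At 2, a group of 128 expects 128 × 2/98 × 90/182.5 = 1.3 events in 90 days, and the size is 0.02% or less.
- *Twice the pilot rates:* 90-day admissions then have a mean of 0.091 and a size of about 6% (k = 2) to 9% (k = 5). 90-day ED reaches about 15% at k = 5.
- *Three controls per participant:* 90-day admissions reach about 5% at k = 5.
- *Other tests:* with a likelihood-ratio test, 90-day admissions run from 6.7% (k = 0) to 9.6% (k = 5). Part of that excess is sparsity, since it is present without overdispersion.

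The longitudinal model was not quantified, because its correlation structure is not stated.

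**The case against.** The strongest reply is that this is an unstated detail in a short methods text, not a demonstrated wrong analysis. A robust variance may have been used, and the word longitudinal may imply some handling of repeated measures. The effect is also modest: the model quoted first adjusts for prior use, three of its four 90-day ED cells lie between 5.2 and 5.9%, and the 7.8% needs frailty variance 5 with no pair correlation. In the adjusted cell (2, 0.6), clustering gives 5.3% against 5.2%, so nothing is gained there. The unadjusted outcome differences are already tested with methods chosen for matching. All of this stands and limits the size of the point.

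It does not remove the point. The direction of the error turns on the outcome form, which is open for admissions as well as ED visits: one sentence applies the same models and the same word, risk, to both.

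A reader might infer that only 90-day ED visits are affected and that sparse events are the sole limit elsewhere. The documents do not support that. The pilot counted diabetes-related events, the planned outcome carries no such limit, and Phase 2.0 adds patients with ED or inpatient encounters, so rates could be higher. Lower rates are equally possible, given the pilot's post-baseline counts. A reader might also infer that ignoring the matching inflates the error; positive pair correlation alone does the opposite.

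**Conclusion.** The point holds in conditional form. The SAP's Poisson models state no allowance for overdispersion or matched sets, and the form of the hospital and ED outcomes is unsettled. If the outcomes are overdispersed counts and the default variance was used, 90-day ED visits are the most exposed at pilot baseline rates: about 5-10% unadjusted and 5-8% adjusted for prior use, against a nominal 5%. That rests on 128 pairs, a Wald test and an assumed frailty variance of 2 to 5. Inflation is immaterial at variance 0 to 1 and absent at the pilot's post-baseline ED rates. It extends to 90-day admissions at about twice the pilot rate.

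The documents do not show that the published intervals are too narrow, nor which variance was used. The change is worth making because it is cheap and protects in both directions; confidence in the size is moderate at best.

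**What to change.** 1. Reconcile the protocol's random selection of controls with the SAP's matching, and state the matching ratio.
2. Keep the Poisson mean model. In all utilization models use a sandwich variance clustered on the matched set, or on the patient if controls are not matched.
3. State for each hospital and ED outcome whether it is a count (rate ratio) or any visit (risk ratio).
4. Report event counts per group, so that precision is judged from the observed data and not assumed in advance.
5. Optionally, add a negative binomial model as a sensitivity analysis for counts.

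The cost is one or two SAP sentences, a variance option in the software already named, and a small rerun. Some intervals will widen slightly: for 90-day ED counts the median ratio of clustered to default standard error was 1.02 to 1.15 across the four simulated cells. The sandwich variance does not cure very sparse outcomes, such as 30-day admissions at pilot rates.

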There is an association between time and urgent PCP visits and ED visits. This means that for those patients enrolled in the program there appears to be a reduction over time in urgent PCP visits and ER visits following program completion. The number of hospitalizations was low overall and does show a trend for reduction over time.

Summary of Findings.

This pilot evidence demonstrates a significant impact on glycemic control and healthcare utilization measures as the result of a concise, focused DM education and medication management intervention.

Phase 2.0 MedStar Diabetes Pathway Expanded Pilot

Building on the success of the MDP Phase 1.0 pilot, the next steps in expanding the program will be as follows:

- **Transition** of the Pathway from early feasibility pilot to the next phase as an expanded pilot program integrated within the MedStar Health System care delivery network and built upon a sustainable infrastructure (brick and mortar –plus- virtual components) across early adopter MMG practice sites.
- **Expand recruitment** to include high risk patients with uncontrolled type 2 diabetes, including those with a new diagnosis and A1C >9%, who have MedStar Emergency Department and/or Inpatient encounters
- **Spread** to additional targeted MedStar Medical Group (A&B) Primary Care Practices and/or to MedStar Managed Care Plan participants (MedStar Family Choice, MedStar Select)

As the MDP is transitioning into a clinical program offered at various MedStar sites, the MDP clinical team is reviewing the data collected during the pilot to improve the program and adapt it to various clinical settings in order to better serve the target patient population. It will be imperative to continue reviewing patient clinical outcomes as the program expands in order to insure continuous quality improvement of the program. This will be achieved through chart reviews of patients receiving diabetes care via the MDP.

III- Chart Review and Data Collection

MDP patients' chart review:

MDP target population:

Inclusion Criteria

- Active and established patient of a MedStar Medical Group Ambulatory Primary Care practice provider:
- Diagnosis of type 2 diabetes on EMR problem list for ≥ 1 year
- New diagnosis of type 2 diabetes with $A1C \geq 9$
- Active practice patient as evidenced by one or more visits to PCP in the past 12 months
- Age ≥ 21 to < 75 years
- $A1C \geq 9.0\%$ at their last visit to MedStar Medical Home, ED or hospital admission.

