- Primary Care Provider willing to have patient enter the program
- Patient is able and willing to participate in the program
- Proficient in English

-AND- one or more of the following high risk characteristics:

- Acute care encounter(s) including) ED visit(s) or hospital admission(s) in the past year with uncontrolled diabetes (BG > 200mg/dL or A1C >9%; severe hypoglycemia = BG <40mg/dL requiring assistance to treat)
- Evidence of low medication adherence as evidenced by no refills since one or more prescribed DM RXs “ran out” (based on last Rx for each DM med and time period was prescribed for on EMR/SureScripts medications list); or any other circumstance that has

been identified by the health care team which indicates poor adherence to prescribed medication.

- Does not meet HEDIS diabetes measures for two or more of: no MA/Cr, no DM retinal exam, no lipid profile
- SBP \geq 140 mmHg
- LDL \geq 100 mg/dL
- Depression diagnosis on problem list (*or depression medication on med list*)
- BMI >32

Exclusion Criteria

- Known history of DKA
- No MedStar PCP visit within past 12 months
- Endocrine or Diabetes Education consult referral order in the past 6 months which resulted in Endo visit(s) or DSME visit(s) documented in chart or self-reported by patient during initial screen
- Active additional medical issues which in the opinion of the care team would preclude concentrating on BG control and/or would predispose to ED visits and/or hospital admits independent of glycemic control, e.g.: severe CHF, severe COPD; severe mental illness.
- Resident of skilled nursing facility, nursing home or receiving home health care services.
- Active cancer in the preceding 3 years excluding nonmalignant basal cell cancer
- Supraphysiologic doses of glucocorticoids (hydrocortisone > 30mg/day; prednisone > 5-6mg daily; dexamethasone > 2mg daily).
- Pregnant or anticipates attempting conception in the following year
- Patient and/or custodial caregiver unwilling and/or unable to participate in program-related activities

The following data will be collected retrospectively from the charts of patients that complete the MDP.

- Demographics
- A1C baseline, at 3 month after baseline visit to assess impact of the pathway.
- Hypoglycemic events (BG<70 and <40) during the 6 months of enrollment in MDP
- Diabetes 2 go Knowledge test
- ED and hospital visits in 30 days and 90 days prior to and after the boot camp
- Referring MedStar Provider satisfaction with intervention

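### The savings projection applies one employee-plan price for diabetes-associated admissions to admissions of undefined cause in a wider payer population, and carries no uncertainty

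*SAP*

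**What the plan says.** The last paragraph of the SAP describes the projection in three steps.

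- **Quantity.** "Based on the expected times of hospitalization per patient in 90 days for both the intervention group and comparison group", as estimated by the Poisson regression model, the SAP projects the yearly difference in inpatient use between a patient with and a patient without the intervention. The adjusted Poisson models earlier in the SAP are used to "estimate post-intervention 30-day and 90-day hospital admission and ED visit risk for participants compared to controls". No cause of admission is given in either place.
- **Price.** The projected change is "multiplied by the expense per diabetes associated hospitalization". The unit price is $25,162.95, calculated from claims of the "employee health plan in Year 2017".
- **Product.** The documents describe no adjustment of the price for payer, no range for the price and no interval for the dollar result.

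The Protocol's data list (section III, Chart Review and Data Collection) names "ED and hospital visits in 30 days and 90 days prior to and after the boot camp", again without a cause. The only cause wording is in the account of the pilot (section I, Health Resource Utilizations), where the list of events ends with "hospitalizations, and Emergency Department (ED) visits due to diabetes".

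On payer, three places in the Protocol show a population wider than the employee plan. Insurance group was a matching factor in the pilot. The Phase 2.0 section plans to spread the program to further primary care practices and/or "MedStar Managed Care Plan participants". The reporting paragraph of section III foresees percentages by type of insurance.

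**The concern.** A unit price can be multiplied by a count only if both refer to the same kind of event in the same kind of patient. Here the price is specific in two ways: diabetes-associated admissions, and one employer's plan in one year. The count is specific in neither. It covers program patients and controls from several insurance groups, and its cause is not stated.

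The projection is offered as a way to put a value on reduced inpatient services for the health system. What one plan's claims show per admission need not equal what the system saves when another payer covers the patient, and the SAP does not discuss this. Any gap between the stated price and the mean cost of the admissions actually counted passes in full proportion into the saving.

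A second weakness compounds the first. The rule yields one point figure. It reflects neither the sampling error in the admission difference nor the doubt about the price, although the price is given to the cent.

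**Working it through.** **Inputs**

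- Unit price *C* = $25,162.95 (SAP, last paragraph).
- Difference *D* in expected hospitalizations per patient in 90 days: not given. Assumed here at 0.01, 0.05 and 0.10.
- Annual factor *k*: not given. Either 4 or 365/90 = 4.056.
- Ratio *r* of the mean cost of the admissions counted to *C*: not given. Assumed range 0.6 to 1.4. The SAP's rule amounts to *r* = 1.

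**Can the plan's own figures be reproduced?** No. The price would need the number of admissions and total expense in the claims data. The saving would need the two 90-day expectations from the model. Neither is in the documents, so only the structure can be checked.

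**Structure.** Saving per patient-year = *D* × *k* × *C* × *r*.

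At *D* = 0.01 and *r* = 1:

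- *k* = 4: 0.01 × 4 × 25,162.95 = $1,007
- *k* = 365/90: 0.01 × 4.056 × 25,162.95 = $1,020

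The choice of factor moves the result by only 1.4% (4.056/4 = 1.014).

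**Effect of the price and of the admission difference** (*k* = 365/90, all values of *D* and *r* assumed):

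| *D* per 90 days | *r* = 0.6 | *r* = 1.0 | *r* = 1.4 |
|---|---|---|---|
| 0.01 | $612 | $1,020 | $1,429 |
| 0.05 | $3,061 | $5,102 | $7,143 |
| 0.10 | $6,123 | $10,205 | $14,287 |

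For scale, the pilot's Table 2 shows 9 hospitalizations in the six months before baseline. Among its 98 patients that is 9/98 = 0.092 per patient, or about 0.046 per 90 days after halving. A difference of 0.10 would exceed that whole rate. The pilot rate may not carry over, because recruitment is to be widened to patients with emergency department or inpatient encounters.

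**Uncertainty in the count.** If the 95% limits of *D* are *L* and *U*, the limits of the saving at a fixed price are *L* × *k* × *C* and *U* × *k* × *C*. Each 0.01 of interval width is therefore $1,020 of width in the saving, and an interval for *D* that includes zero gives a saving that includes zero. The pilot's p value for hospitalizations was 0.207 on small counts, so this input may well be imprecise.

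**Cause of admission, passages side by side.** The pilot definition mentions diabetes, with six-month look-back windows. The ongoing data list uses 30- and 90-day windows and drops the cause. The SAP uses the same 30- and 90-day windows, also without a cause. The exclusion criteria remove patients whose other conditions "would predispose to ED visits and/or hospital admits independent of glycemic control". That narrows the mix of admissions in program patients but does not define the outcome. Controls are described in section III only as randomly selected patients with elevated A1C, and the documents do not say that this exclusion applies to them.

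**The case against.** The strongest reply is that the SAP discloses what it did. It names the plan, the year, the type of admission and the exact price, so a reader with another unit cost can rescale the result. The projection is an added, exploratory look at whether benefits could be monetized, and no clinical comparison depends on it. Using the one claims source at hand is a common simplification. The documents give neither the payer mix of the analysed cohort nor any other price, so nothing shows that the employee-plan figure is wrong for these patients. The dollar amounts above rest on assumed inputs and illustrate proportionality rather than measure a bias.

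Most of this stands. It keeps the point small and rules out any claim about direction. Disclosure of the price does not, however, supply the interval for the admission difference, and a reader cannot rebuild that from a point figure.

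A reader might also infer that the model counts all-cause admissions and that the projection therefore certainly prices the wrong events. The documents do not support that. They never call the count all-cause. The only cause wording, in the pilot, points to diabetes, although it could be read as attaching to emergency visits alone. If the pilot definition carried over, count and price would agree on cause. A mismatch in admission type is a possibility left open by missing wording.

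**Conclusion.** The point holds in limited form. The documents show that a price from one employee plan is applied to a population not confined to that plan, without adjustment, and that the rule as written gives a single dollar figure with no allowance for error in the count or the price. A mismatch in the type of admission is conditional on the count not being restricted to diabetes, which the documents leave undefined.

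The direction and size of any bias are unknown, so a reader should not conclude that the savings are overstated. What can be said is that the result is proportional to both inputs, so the assumed price band of ±40% gives ±40% in the saving whatever the admission difference is. This is a minor improvement to a secondary, exploratory analysis.

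**What to change.** 1. State whether the modelled hospitalizations are diabetes-associated or of any cause, and use the same definition for the price.
2. Estimate the 90-day rate difference with a confidence interval that respects the matching, state the annual factor, and report the annual dollar figure with the corresponding limits.
3. Vary the unit cost over a stated range and show the results in a short table, such as the one above with the fitted difference in place of the assumed ones.
4. Label the result an illustration at employee-plan prices.

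Payer-specific costs weighted by the cohort's insurance mix would be better still, but they need claims data that the documents do not show to be available. Restricting the analysis to employee-plan members is not advised: it would discard an unknown share of the 128 per group and could break matched sets.

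The cost is a few sentences in the SAP and one small table, and possibly one further claims query if the price has to be recomputed under a different admission definition. The downside is a wider and less striking savings figure.
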